11.4.1.3. Study Phases for Concomitant Medication

Study Phase	Definition
Prior	If medication end date is not missing and is before the first treatment date
Concomitant	Any medication that is not a "prior"

NOTES:

CONFIDENTIAL

204947

Study Phase	Definition
-------------	------------

- Please refer to [Appendix 7](#): Reporting Standards for Missing Data for handling of missing and partial dates for concomitant medication. Use the rules in this table if concomitant medication date is completely missing.
- The definition of "prior" for prior OAB medication is different from above definition, in accordance with study protocol.

CONFIDENTIAL

204947

11.4.2. Treatment Emergent Flag for Adverse Events

Treatment emergent flag for AEs is not defined in this study.

11.5. Appendix 5: Data Display Standards & Handling Conventions

11.5.1. Reporting Process

Software	

 The currently supported versions of SAS software will be used. 	
Reporting Area	
HARP Server	: US1SALX00259
HARP Compound	[for interim analyses]: arenv/arprod/gsk1358820/mid204947/primary [for final analyses]: arenv/arprod/gsk1358820/mid204947/final
Analysis Datasets	

 Analysis datasets will be created according to Legacy GSK A&R dataset standards. . 	
Generation of RTF Files	

 RTF files will not be generated. 	

11.5.2. Reporting Standards

General	

 The current GSK Integrated Data Standards Library (IDSL) will be applied for reporting, unless otherwise stated (IDSL Standards Location: https://spope.gsk.com/sites/IDSLLibrary/SitePages/Home.aspx): 
 4.03 to 4.23: General Principles 5.01 to 5.08: Principles Related to Data Listings 6.01 to 6.11: Principles Related to Summary Tables 7.01 to 7.13: Principles Related to Graphics Do not include subject level listings in the main body of the GSK Clinical Study Report. All subject level listings should be located in the modular appendices as ICH or non-ICH listings 	
Formats	

 GSK IDSL Statistical Principles (5.03 & 6.06.3) for decimal places (DP's) will be adopted for reporting of data based on the raw data collected, unless otherwise stated. Numeric data will be reported at the precision collected on the eCRF. The reported precision from non eCRF sources will follow the IDSL statistical principles but may be adjusted to a clinically interpretable number of DP's. 	
Planned and Actual Time	

 Reporting for tables, figures and formal statistical analyses: 
 Planned time relative to dosing will be used in figures, summaries, statistical analyses and calculation of any derived parameters, unless otherwise stated. The impact of any major deviation from the planned assessment times and/or scheduled visit days on the analyses and interpretation of the results will be assessed as appropriate. Reporting for Data Listings: 
 Planned and actual time relative to study drug dosing will be shown in listings (Refer to IDSL Statistical Principle 5.05.1). Unscheduled or unplanned readings will be presented within the subject's listings. 	
Unscheduled Visits	

 Unscheduled visits will not be included in summary tables and/or figures. All unscheduled visits will be included in listings. 	

CONFIDENTIAL

204947

Descriptive Summary Statistics	
Continuous Data	Refer to IDSL Statistical Principle 6.06.1 N, mean, standard deviation (or standard error), median, minimum and maximum.
Categorical Data	N, n, frequency, %
Graphical Displays	
• Refer to IDSL Statistical Principals 7.01 to 7.13.	

11.6. Appendix 6: Derived and Transformed Data

11.6.1. General

Multiple Measurements at One Analysis Time Point

 Mean of the measurements will be calculated and used in any derivation of summary statistics but if listed, all data will be presented. If there are two values within a time window (as per Section 11.3.1) the value closest to the target day for that window will be used. If values are the same distance from the target, then the value for the earlier date will be taken. Participants having both High and Low values for Normal Ranges at any post-baseline visit for safety parameters will be counted in both the High and Low categories of "Any visit post-baseline" row of related summary tables.
Study Day

 Calculated as the number of days from First Dose Date: 
 Ref Date = Missing → Study Day = Missing Ref Date < First Dose Date → Study Day = Ref Date – First Dose Date Ref Date ≥ First Dose Date → Study Day = Ref Date – (First Dose Date) + 1

11.6.2. Study Population

Duration of Follow-Up instead of Extent of Exposure			

 Number of days of follow-up after study drug administration will be calculated based on the formula by Overall and TCs: 			
$\text{Duration of Follow-Up in Days} = \text{Date X} - (\text{Date Y}) + 1$			
For subjects who received GSK1358820 as first treatment			
Overall / TC for calculation	Subject status	X	Y
Overall	All subjects	Study Exit / Withdraw Date	1st treatment date
TC1	Study Exit or Withdraw in TC1	Study Exit / Withdraw Date [1]	1st treatment date
TC1	Receive next treatment	Date prior to 2nd treatment [1]	1st treatment date
GTC1	The same days as TC1		
GTC2	Study Exit or Withdraw in TC2	Study Exit / Withdraw Date	2nd treatment date
GTC2	Receive next treatment	Date prior to 3rd treatment	2nd treatment date
GTC3	All subjects in GTC3	Study Exit / Withdraw Date	3rd treatment date
For subjects who received Placebo as first treatment			
Overall / TC for	Subject status	X	Y

Duration of Follow-Up instead of Extent of Exposure					
calculation	All subjects	Study Exit / Withdraw Date	2nd treatment date (1st treatment date of GSK1358820)		
	Overall				
	TC1	Study Exit or Withdraw in TC1	Study Exit / Withdraw Date [1]		
	TC1	Receive next treatment	Date prior to 2nd treatment [1]		
	GTC1	Study Exit or Withdraw in GTC1	Study Exit / Withdraw Date		
	GTC1	Receive next treatment	Date prior to 3rd treatment		
	GTC2	All subjects in GTC2	Study Exit / Withdraw Date		
	GTC3	Not applicable, because GSK1358820 treatment is allowed only two times for subjects who received Placebo as first treatment in this study.			

 [1] In interim analysis, use the following date: 
 Date of withdraw date for subjects who do not receive 2nd treatment and withdraw before week 24 after 1st treatment Date of the Week 24 visit in treatment phase 1 for subjects who do not receive 2nd treatment and do not withdraw Date prior to 2nd treatment for subjects who receive 2nd treatment at the Week 12 / 18 visit in treatment phase 1 					
Duration of OAB history					

 Duration of OAB history is defined as the duration (years) from the date of diagnosis to the date of screening visit. 					

Identification of BPH

 Since information of BPH was collected as current medical conditions as text data, it is needed to identify which texts will be regarded as BPH. Following texts in current medical condition should be regarded as BPH. Texts may be uppercase or lowercase letter. 
 benign prostatic hyperplasia benign prostatic hypertrophy bph hyperplasia of prostate prostate hypertrophy prostatic hyperplasia prostatic hypertrophy prostatic hypertrophy(benign)

Identification of anticholinergic drug and beta-3 agonist

- Since information of anticholinergic drug and beta-3 agonist was collected as 'prior OAB medication', it is needed to identify which codes will be regarded as anticholinergic drug and beta-3 agonist. Following code will be in SI dataset

Drug	Term Name	Code
Anticholinergics	FESOTERODINE	54026501
	FESOTERODINE FUMARATE	54026502
	IMIDAFENACIN	53735601
	OXYBUTYNIN	00538901
	OXYBUTYNIN HYDROCHLORIDE	00538902
	PROPIVERINE	01241601
	PROPIVERINE HYDROCHLORIDE	01241602
	SOLIFENACIN	53085701
	SOLIFENACIN SUCCINATE	53085702
	TOLTERODINE	01350201
	TOLTERODINE TARTRATE	01350202
	TOLTERODINE FUMARATE	01350203
beta-3 adrenergic receptor agonist	MIRABEGRON	54321501

[figure not shown]
11.6.3. Efficacy

Diary Data Convention
General Convention

 For baseline and post-treatment visits, analyses will be based on the diary data collected during a 3-day interval for each visit. Each 3-day interval consists of 3 consecutive 24-hour periods, with the first period starting from the time of the first urinary episode on the first of the 3 days. A valid diary day is defined as any of the three 24-hour periods with 2 or more any type of urinary episodes. Data collected from a 24-hour period with less than 2 urinary episodes (i.e., an invalid diary day) will be set to missing in this day. For baseline and post-treatment visits, the 3-day diary will be determined based on the following algorithm: 
 Apply assessment windows defined in Section 11.3.1, which are based on days from the date of study treatment. Determine the time of the first urinary episode that is within the assessment window (in the example below, 7:30am on Apr3). Count forwards for 3 consecutive days (in

Diary Data Convention

the example below, APR3 is considered as 7:30am on Apr3 to 7:29am on APR4, APR4 is considered as 7:30am on Apr4 to 7:29am on APR5 and APR5 is considered as 7:30am on Apr5 to 7:29am on APR6 for diary data handling). As for volume voided, the time of the first collection of volume voided should be determined independently of the time of the first urinary episode. Note: the last 24-hour period should end within the window, i.e., prior or on the last day specified in the window definition; otherwise, the 24-hour data will not be used for the corresponding window. For baseline diary data, the urinary episodes that occurred on injection day but before the injection time will be counted for baseline diary data.

- Using the example below, the first 24-hour time period starts from 7:30am on Apr 3 and ends at 7:29am on Apr 4. The second 24-hour time period starts from 7:30am on Apr4 and ends at 7:29am on Apr 5. Note that this 24-hour is considered an as invalid diary day since it has only one episode during the 24 hours. The third or the last 24-hour time period starts from 7:30am on Apr 5 and ends at 7:29am on Apr6.
- At least one valid 24-hour diary day within the window is required for the visit. Otherwise, the 3-day diary data will be missing for the visit.

For diary data with a diary date but missing the urinary time, the diary time will be set to mid-day at 12:00pm.

Example for date of diary data handling

- Here, the example of handling of diary data of 3 consecutive days and its relation to assessment window is described for the case of TC1 week 12.
- As shown in [11.3.1](#), the target data of TC1 week 12 is day 85 and the assessment window of TC1 week 12 is from day 65 to day 106. The time of the first urinary episode should be within day 65 to day106 for diary data of TC1 week 12. In addition, only the data until day106 is available for TC1 week12.
- All examples below are assumed that valid diaries were taken for 3 consecutive days.
- In example 1, the first day is not from day 65 to day 106. Therefore, all the diary data for this visit are NOT available for TC1 week12.
- In example 2 and 3, all diary data are available because diary date for data handling are from day 65 to day 106.
- In example 4 and 5, a part of diary date for data handling is out the range (day 65-106). Diary of these days are regarded as invalid diary.

Diary Data Convention				
Example number	The time of the first urinary episode	After 3 consecutive 24-hour period (3 consecutive days)	Diary date for data handling	Available data for diary data of TC1 week 12
1	Day 64 9:00am	Day 67 8:59am	Day 64, 65, 66	No data available
2	Day 65 9:00am	Day 68 8:59am	Day 65, 66, 67	All data available
3	Day 104 9:00am	Day 107 8:59am	Day 104, 105, 106	All data available
4	Day 105 9:00am	Day 108 8:59am	Day 105, 106, 107	Day 105 and 106 are available
5	Day 106 9:00am	Day 109 8:59am	Day 106, 107, 108	Only day 106 is available

Derivation of diary endpoints				

 Following endpoint will be derived as "A" divided by "B". "A" and "B" are defined below for each endpoint. Derivation should be done by visit. These derivations will be done by using only diary data in valid diary days. 				

For valid diary day, if no episodes are recorded, "A" on that day will be treated as zero.

Endpoint	A	B
Daily average number of urinary incontinence episodes	Number of "Yes" response to the diary question of "Did you have accidental urinary leakage?"	Number of valid diary days in the visit
Daily average number of urinary urgency incontinence episodes	Number of ("Yes" response to the diary question of "Did you have accidental urinary leakage?") AND ("Yes" response to the diary question of "Was this episode associated with a sudden and urgent need to urinate?") in the same record	
Daily average number of voids	Number of "Yes" response to the diary question of "Did you urinate into the toilet?"	
Daily average number of urgency episodes	Number of "Yes" response to the diary question of "Was this episode associated with a sudden and urgent need to urinate?"	
Daily average number of nocturia episodes (voids that	Number of "Yes" response to the diary question of "Did this	

Diary Data Convention		
interrupt night sleep)	episode wake you from night sleep?"	
Daily average number of severe urgency episodes	Number of "3-Severe Urgency" response to the diary question of "How would you rate your need to urinate?"	
Daily average number of severe or moderate urgency episodes	Number of "3-Severe Urgency" or "2-Moderate Urgency" response to the diary question of "How would you rate your need to urinate?"	
Average volume voided per micturition	The total volume collected in 24-hour period	Number of the urinary volume records which are not missing

 For the endpoint of Proportion of patients attaining 100%, $\geq 75\%$ and $\geq 50\%$ reduction from baseline in the daily average of urinary (urgency) incontinence episodes, if change from baseline in the daily average of urinary (urgency) incontinence episodes 
 is -100%, then this subject will attain 100%, $\geq 75\%$ and $\geq 50\%$ falls the range (-100 < , $\leq -75\%$), then this subject will attain $\geq 75\%$ and $\geq 50\%$ falls the range (-75 < , $\leq -50\%$), then this subject will attain $\geq 50\%$ is larger than -50%, then this subject will not attain any category 		

 For Proportion of subjects with maximum urgency intensity and Change from baseline of maximum urgency intensity, "maximum" will be defined as the maximum urgency intensity within 3-day period (but only for valid diary day) in the visit. This will be derived as one record per one visit. 		
Handling of partial missing data in diary (except for urinary time)		

 If the response to the diary question of "How would you rate your need to urinate?" is missing, then do; 
 If the response to the diary question of "Was this episode associated with a sudden and urgent need to urinate?" is "Yes", the above response will be imputed as "3-Severe Urgency". If the response to the diary question of "Was this episode associated with a sudden and urgent need to urinate?" is "No", the above response will be imputed as "0-No Urgency". If the response to the diary question of "Was this episode associated with a sudden and urgent need to urinate?" is missing, the above response will be treated as missing. If the response to the diary question of "Record volume collected OR indicate "not collected" for each episode" is missing, then this response will be treated as missing, not zero of volume. 		

Diary Data Convention

 As for other response, the missing response will be treated as missing. In other words, this is the same meaning to be treated as "No" to the response to the diary question.
Handling of missing urinary time

 For diary data with a diary date but missing the urinary time, the diary time will be set to mid-day at 12:00 pm at that day.
Handling of partial missing day in diary

 Partial missing day is defined as any missing diary day or invalid diary day in 3-day period. If there are 1 or 2 partial missing days in 3- day bladder diary, these days will be treated as missing and no imputation will be done for partial missing day. Therefore, endpoints in 3- day bladder diary will be calculated by using 1 or 2 valid diary data, if there is any partial missing day in the visit.
Definition of Incomplete 3-day diary

 Incomplete 3-day diary is defined as the diary which does not have 3 valid diary days.

KHQ and OABSS Convention				
Derivation of KHQ domains				
Following table shows the derivation of KHQ domains [Committee for Preparation of the Clinical Guideline for Overactive Bladder, the Japanese Continence Society, 2015]. Only role limitations and social limitations will be analysed by ANCOVA model. Other domains will be only summarized.				
Domain	ITEMS	Question in eCRF	scale	Derivation
General Health Perception	1 (1 item)		1= Very Good 2= Good 3= Fair 4= Poor 5= Very Poor	Domain Score = $(\text{score of left item} - 1) / 4 * 100$
Incontinence Impact	2 (1item)		1= Not at all 2= A little 3= Moderately 4= A lot	Domain Score = $(\text{score of left item} - 1) / 3 * 100$
Role Limitations	3a and 3b (2 items)		1= Not at all 2=Slightly 3=Moderately 4=A lot	Domain Score = $(\text{summed scores of left items} - 2) / 6 * 100$
Physical Limitations	4a and 4b (2 items)		1= Not at all 2=Slightly 3=Moderately 4=A lot	Domain Score = $(\text{summed scores of left items} - 2) / 6 * 100$
Social Limitations	4c, 4d, 5c (3 items)		0= N/A 1= Not at all 2=Slightly 3=Moderately	Domain Score = $(\text{summed scores of left items} - 3) / 9 * 100$ If score of 5c = 0 then

KHQ and OABSS Convention				
Derivation of KHQ domains				
			4=A lot	Domain Score = (summed scores of left items -2) / 6 * 100
Personal Relationships	5a and 5b (2 items)		0= N/A 1= Not at all 2=Slightly 3=Moderately 4=A lot	Domain Score = (summed scores of left items -2) / 6 * 100 If summed scores of left items = 1 then Domain Score = (summed scores of left items -1) / 3 * 100 If summed scores of left items = 0 then Domain Score will be treated as missing
Emotions	6a, 6b and 6c (3 items)		1= Not at all 2=Slightly 3=Moderately 4=Very Much	Domain Score = (summed scores of left items -3) / 9 * 100
Sleep/Energy	7a and 7b (2 items)		1= Never 2=Sometimes 3=Often 4=All the time	Domain Score = (summed scores of left items -2) / 6 * 100
Severity/Coping Measures	8a, 8b, 8c, 8d and 8e (5 items)		1= Never 2=Sometimes 3=Often 4=All the time	Domain Score = (summed scores of left items -5) / 15 * 100
Derivation of OABSS total score				
OABSS total score will be calculated as the sum of scores for following questions [Homma, 2006].				
Question	Answer (Frequency)		Score	
How many times do you typically urinate from waking in the morning until sleeping at night?	≤ 7		0	
	8-14		1	
	≥ 15		2	
How many times do you typically wake up to urinate from sleeping at night until waking in the morning?	0		0	
	1		1	
	2		2	
	≥ 3		3	
How often do you have a sudden desire to urinate, which is difficult to defer?	Not at all		0	
	Less than once a week		1	

CONFIDENTIAL

204947

KHQ and OABSS Convention		
Derivation of KHQ domains		
	Once a week or more	2
	About once a day	3
	2-4 times a day	4
	5 times a day or more	5
How often do you leak urine because you cannot defer the sudden desire to urinate?	Not at all	0
	Less than once a week	1
	Once a week or more	2
	About once a day	3
	2-4 times a day	4
	5 times a day or more	5
•		
Handling of partial missing data		

 • If missing data exists in KHQ and OABSS data in the visit, the corresponded item or domain will be treated as missing. 		

TBS
Answers and positive response of TBS

TBS (treatment benefit scale) consists of 4 answers to 1 questions "Please complete the following question by considering your current condition (urinary problems, urinary incontinence) compared to your condition before you received any study treatment in this trial". Subjects will select their answer to this question considering their condition. Available answers are below and will be coded 1 to 4 in order to use statistical analysis.
 
 • 1 - Greatly improved • 2 - Improved • 3 - Not changed • 4 - Worsened 
The answers of 1 – Greatly improved or 2 – Improved will be regarded as positive response.
 
Other answers including missing data will be regarded as NO positive response.

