## 7.3. Efficacy

### 7.3.1. Methods of assessments

#### 7.3.1.1. Bladder diary

The subjects will be instructed to enter data on the bladder diary over 3 consecutive days as specified below. When receiving the diary, the subjects will be instructed and trained on the use of the diary and the data to be collected (See SRM and bladder diary). The subjects are instructed to bring their diary to each clinic visit. The diary data will also be used to satisfy eligibility requirements for study entry as well as to qualify the subject for re-treatment. The bladder diary will be treated as a source document and archived with the medical record. The staff involved in the study at the study site will send the copy of bladder diary to the sponsor after confirming that no personal information is contained in the diary (see SRM for method of forwarding).

[Period to enter data in the bladder diary]

- Screening phase: Enter data on the bladder diary over 3 consecutive days during the screening phase within 28 days prior to Treatment phase 1. However, the day of initiation of Treatment phase 1 (week 0) should not be included in the data-entry period.
- Treatment phase 1 and Treatment phase 2: Enter data on the bladder diary over 3 consecutive days within a week prior to each scheduled visit. However, the day of scheduled visit should not be included in the data-entry period.

The diary will capture the following information:

- Date and time of urinary episode (including urinary incontinence)
- Episodes of micturition (toilet voids)
- Episodes of urinary incontinencea
- Episodes of urgency

- Intensity of urgency

In answer to the question “how would you rate your need to urinate (urgency)?” in the bladder diary, the subjects will be asked to select one of the following 4 options:

0 – No urgency. I felt no need to empty my bladder, but did so for other reasons.

1 – Mild urgency. I could postpone urinating as long as necessary without fear of wetting myself.

2 – Moderate Urgency. I could postpone urinating for a short while without fear of wetting myself.

3 – Severe Urgency. I could not postpone urinating, but had to rush to the toilet in order not to wet myself.

- Episodes of nocturia (voids that interrupt night sleep)

- Use of CIC

- Urine volume

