The total volume voided will be measured and recorded by subjects over one 24-hour period during the 3-day bladder diary collection period (urine volume of urinary incontinence will not be measured and recorded). To perform this measurement, urine collection containers provided by the sponsor will be used. The volume voided per micturitionb will be determined by the sponsor from the total urine volume measured by the subjects divided by the number of micturitions (excluding urinary incontinence episode).

If a subject has symptoms of a urinary tract infection, the diary data will not be collected during this period because the data may have influence on the bladder diary data.

a: used for evaluation of primary endpoint (Change from baseline in the daily average number of urinary incontinence episodes a at week 12 after the first treatment)

b: used for evaluation of major secondary endpoint (Change from baseline in the average volume voided per micturition at week 12 after the first treatment)

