7.3.1. Endpoint / Variables

- Changes from baseline and percentage change from baseline in the following endpoints
 - Daily average number of urinary incontinence episodes
 - Daily average number of urinary urgency incontinence episodes
 - Daily average number of voids
 - Average volume voided per micturition
 - Daily average number of urgency episodes
 - Daily average number of nocturia episodes (voids that interrupt night sleep)
- Urgency intensity
 - Change from baseline in daily average number of urgency episodes by each urgency intensity category
 - Proportions of patients with maximum urgency intensity
 - Change from baseline of maximum urgency intensity
- Proportion of patients attaining 100%, $\geq 75\%$ and $\geq 50\%$ reduction from baseline in the daily average of urinary incontinence episodes
- Proportion of patients attaining 100%, $\geq 75\%$ and $\geq 50\%$ reduction from baseline in the daily average of urinary urgency incontinence episodes
- Duration of treatment effect after 1st treatment
 - Time to qualification for retreatment
 - Time to request for retreatment
- Health outcome
 - Changes from baseline in King's Health Questionnaire (KHQ) domain scores
 - Proportion of patients with positive response on the Treatment Benefit Scale (TBS)
 - Changes from baseline in Overactive Bladder Symptom Score (OABSS) total score

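### SAP 11.6.3 counts every episode that wakes the patient as nocturia, although the endpoint is defined as voids, so a waking leak without a void is included

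*SAP*

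**What the plan says.** The definition is the same wherever it appears. Protocol 7.3.1.1 lists the diary item as "Episodes of nocturia (voids that interrupt night sleep", and SAP 7.3.1 lists the endpoint as "Daily average number of nocturia episodes (voids that interrupt night sleep".

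The derivation table in SAP 11.6.3 repeats that label in its row "Daily average number of nocturia episodes (voids that", but the numerator is only the number of yes answers to the question that asks whether this "episode wake you from night sleep". The denominator is the number of valid diary days. No void condition is attached.

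Whether a void took place is a separate item. The numerator for the voids endpoint is the number of yes answers to the "diary question of 'Did you urinate into the toilet". For urgency incontinence, the same table does combine two answers: leakage and urgency must both be yes "in the same record".

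Nocturia is an other secondary endpoint. Under SAP 7.3.5.1 it is analysed by MMRM to week 12 and by ANCOVA afterwards, with treatment differences, confidence intervals and p-values. SAP 5.5 applies no multiplicity adjustment to it.

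**The concern.** A diary record need not be a void. Protocol 7.3.1.1 has the diary capture "Date and time of urinary episode (including urinary incontinence", and it keeps the two kinds of episode apart when it derives volume per micturition, which is total volume "divided by the number of micturitions (excluding urinary incontinence episode". Taken literally, the SAP rule therefore counts as nocturia a leak that wakes the patient and is not followed by a void in the same record.

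At stake is whether the nocturia result measures what its label says. The drug is expected to reduce leakage. If waking leak-only records exist and fall more on active than on placebo, the nocturia count falls more on active even when waking voids do not change. The nocturia result would then partly repeat the incontinence result. Adjustment for baseline would not remove this, because the difference arises after treatment.

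**Working it through.** **1. Is the void restriction restored anywhere else?** I found no place that does so.
- The general diary conventions in SAP 11.6.3 restrict derivations to valid diary days, and a valid day is judged on urinary episodes of any type.
- The table of changes from the protocol (SAP 2.1) mentions nocturia only for the analysis of percent change.
- The April 2018 SAP has the same derivation, and the July 2018 amendment log (SAP 1.1) does not touch it.

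**2. What the rule does to a record.** Take three valid days, each night with one waking void and one waking leak-only record.
- As written: 6 waking records / 3 days = 2.0 per day.
- With a void also required: 3 / 3 = 1.0 per day.

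If one awakening is logged as a leak record and a separate void record, both marked as waking, the present rule counts it twice.

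**3. Size, first illustration.** The documents give no nocturia rate, SD or power, so there is no plan figure to reproduce. Every input here is an assumption: 2.0 waking episodes per night, a share s of them leak-only, and leak-only episodes falling 60% on active and 20% on placebo.

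Extra difference = 2.0 × s × (0.60 − 0.20) = 0.80 × s

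| s | Extra difference per night |
|---|---|
| 0 | 0 |
| 5% | 0.04 |
| 10% | 0.08 |
| 20% | 0.16 |

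**4. Size, second illustration.** This one starts from the incontinence difference of −1.79 episodes/day and the 120 subjects per group in Protocol 9.2.1. Those inputs reproduce the plan's own power: 97.7% for incontinence and, with 30 mL and SD 70 mL, 91.3% for volume. The joint lower bound is 97.7 + 91.3 − 100 = 89.0%. The protocol states 98%, 91% and 89%.

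Suppose waking voids do not differ between arms and a share q of the 1.79 consists of waking leak-only episodes. Then d = 1.79 × q. For a simple two-sided test, SE = SD × √(2/120) and the chance of p < 0.05 is Φ(d/SE − 1.96) + Φ(−d/SE − 1.96). The nocturia SD of 0.8 to 1.2 and all values of q are assumptions.

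| q | d per day | Chance of p < 0.05 (SD 1.2 to 0.8) |
|---|---|---|
| 0 | 0 | 5% |
| 1% | 0.02 | 5% |
| 5% | 0.09 | 9–14% |
| 10% | 0.18 | 21–41% |
| 15% | 0.27 | 41–74% |

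The answer depends almost entirely on q, which the documents do not give.

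**The case against.** The strongest objection is that the diary form is not in the documents. The mismatch has an effect only if a leak-only record can carry a yes to the waking question. Protocol 7.3.1.1 describes the captured item itself as voids and refers to the study reference manual and the diary for instructions, so the form or the training may tie the waking question to voids. This stands: it leaves the wording of the rule wrong but makes its effect uncertain.

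Two further limits also stand. A patient who wakes, leaks and then reaches the toilet can record leak and void together, and that record counts under either rule. No success criterion rests on nocturia.

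A bare void condition also has costs:
- The diary captures catheter use, but the documents do not say how a waking catheterisation is answered on the toilet question. Retention was 7.1% on 100 U against 0.5% on placebo in the earlier studies (Protocol 4.6.1). Dropping waking catheterisations could therefore remove bladder emptying mainly on active, which would be an error in favour of the drug.
- SAP 11.6.3 treats an unanswered item of this kind as no, so a waking void with a blank toilet answer would be lost.
- A waking leak that becomes a waking void would score as more nocturia although the number of awakenings is unchanged. That follows from the endpoint's own definition.

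A reader might infer that incontinence benefit does leak into the nocturia result and that the effect is overstated. The documents do not support that: they give no rate of waking leak-only records, and that rate could be close to zero.

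**Conclusion.** The derivation does not match the endpoint it is meant to produce, and no other text in either document repairs it. Under the rule as written, waking leak-only records count as nocturia.

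The consequence is conditional. The nocturia treatment difference could be overstated if such records occur and fall more on active. Its size is unknown. It is zero if there are no such records and about 0.16 episodes per night at the top of the first set of assumptions. The second set reaches 0.27 per day at q = 15%. Neither figure is an estimate or an upper bound.

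The point is minor: it concerns one other secondary endpoint with no multiplicity control. The primary and major secondary derivations do not use the waking question and are unaffected.

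**What to change.** In SAP 11.6.3:
- Set the nocturia numerator to records with yes to the waking question and yes to the toilet-void question in the same record.
- Count a waking record with catheter emptying as a void, using the catheter item that the diary already captures, so that the condition does not remove bladder emptying mainly on active.
- Report the count as currently written as a sensitivity analysis. The gap between the two counts would show how much the definition matters.

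Check the diary form first to see whether a leak-only record can be marked as waking and how catheter use is linked to a record.

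The cost is one extra condition, the catheter rule and one additional analysis, with no new data if catheter use can be linked to the record. The remaining downside is small: a waking void with an unanswered toilet item drops out of the main count under the missing-equals-no rule, though the sensitivity analysis still includes it. The week 12 MMRM table for nocturia is scheduled for the interim report (SAP 11.10.6), so the rule should be settled before that unblinding.
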